#### 9.1.2. Prior and Concomitant Medications

During screening, medications used up to 90 days prior to signing informed consent will be solicited. Any medications used within 30 days prior to vaccination through discharge after delivery for pregnant women and the day of life 180 visit for infants (or early termination if prior) will be recorded in the eCRFs.

Summaries of medications that were started prior to dosing and continuing at the time of dosing will be presented by WHO Anatomical Therapeutic Classification (ATC) Levels 1 and 2 and treatment group ([Table 73](#) and [Table 74](#)).

Individual subject listings will be presented for all concomitant medications ([Listing 17](#)).

## 9.2. Measurements of Treatment Compliance

Any subjects who were enrolled but not vaccinated will be presented by treatment group as part of the maternal subject disposition table ([Table 9](#)).

## 9.3. Adverse Events

When calculating the incidence of adverse events (i.e., on a per subject basis), each subject will only be counted once and any repetitions of adverse events within a subject will be ignored; the denominator will be the total size of the specified population being analyzed. All adverse events reported will be included in the summaries and analyses.

An overall summary of adverse events is presented in [Table 45](#) and [Table 46](#).

Adverse events occurring in 5% of subjects in either treatment group will be presented in [Table 47](#) and [Table 48](#).

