The consent process of the pregnant subject will also include permission for inclusion of the infant in the postpartum phase of the study. After participants have given birth, study personnel will review the infant participation with them. After this review, participants will reaffirm their consent for their infants to take part in the post-partum phase of the study by signing the applicable page on the consent form. If this page is not signed, it is assumed that consent is not given and the infant will not participate in the post-partum phase of the study. Separate permission from the father of the infant will not be required, unless individual IRBs or Research Ethics Committees require it. Subject understanding of the study is determined by the research team member who is performing the informed consent process by asking the subject questions and by discussing the study with the subject. No formal Evaluation to Sign Consent or Comprehension Questionnaire will be used.

For illiterate subjects, the consent document will be provided on audiotape with verbatim reading of the consent document in the language understandable to the subject. For illiterate pregnant women, even if the father of the baby is literate, the pregnant woman will provide permission. Whenever possible, the father of the baby will be involved in the decision, but his

signature/fingerprint to confirm permission for the infant participation will not be required, unless the local IRB/Research Ethics Committee requires it.

The consent process for illiterate subjects will require that an impartial witness is present during the consent process and that the witness signs and dates the consent form. The witness must speak the language in which consent is obtained and must not be a key personnel member in the study.

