### **6.3.3. Safety Population**

The Safety Analysis population includes all pregnant women who received the study vaccination, and all infants born during the study.

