## 9. SAFETY EVALUATION

All summaries and analysis of safety data will be presented for the Safety Analysis Population. Safety summaries will be presented overall and by treatment group.

Listings will be sorted by maternal or infant, treatment group, subject ID, parameter (if applicable), and visit.

Continuous variables will be summarized using the following descriptive statistics: n (non-missing sample size), mean, standard deviation, median, maximum and minimum. All categorical measures will be summarized by the frequency and percentages (based on the non-missing sample size) of observed levels. The denominator for the percentages may be based on the number of non-missing observations for an assessment or based on the number of subjects in a population. This will be described for each table.

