### 9.3.2. Unsolicited Adverse Events

The proportion of subjects reporting at least one unsolicited adverse event will be summarized by MedDRA system organ class (SOC) and preferred term (PT).

Unsolicited adverse events by subject will be presented in [Listing 12](#).

The following summaries for unsolicited adverse events will be presented:

- Subject incidence and total frequency of adverse events over time by MedDRA SOC, PT, and treatment group with 95% CI (Days 1-8 Days > 8) ([Table 55](#), [Table 56](#), [Table 57](#), and [Table 58](#));

- Summary of severity and relationship to study product by MedDRA SOC, PT and treatment group ([Table 59](#) and [Table 60](#));
- Subject incidence and total frequency of pregnancy-or infancy related adverse events by treatment group with 95% CI ([Table 77](#) and [Table 78](#));
- Subject listing of non-serious adverse events of moderate or greater severity by MedDRA SOC, PT, and treatment group ([Table 63](#));
- Listing of new onset chronic medical conditions by MedDRA SOC, PT, and treatment group ([Table 64](#));
- Bar chart of the frequency of serious and non-serious related adverse events by severity, MedDRA SOC, and treatment group ([Figure 227](#));
- Bar chart of the incidence of serious and non-serious related adverse events by maximum severity, MedDRA SOC, and treatment group ([Figure 228](#) )

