	Severe									
Myalgia	None									
	Mild									
	Moderate									
	Severe									
Arthralgia	None									
	Mild									
	Moderate									
	Severe									
Headache	None									
	Mild									
	Moderate									
	Severe									

Table 51: Number and Percentage of Maternal Subjects Experiencing Solicited Events by Symptom, Maximum Severity, and Treatment Group (continued)

Symptom	Severity	BOOSTRIX (N=X)			Td (N=X)			All Subjects (N=X)		
		n	%	95% CI	n	%	95% CI	n	%	95% CI
Nausea	None									
	Mild									
	Moderate									
	Severe									
Allergic Reaction	None									
	Mild									
	Moderate									
	Severe									
Fever	None									
	Mild									
	Moderate									
	Severe									
Any Local Symptom	None	x	xx		x	xx		x	xx	
	Mild									
	Moderate									
	Severe									
Pain	None									
	Mild									
	Moderate									
	Severe									
Tenderness	None									
	Mild									
	Moderate									
	Severe									
Ecchymosis	None									
	Mild									
	Moderate									
	Severe									
Erythema	None									
	Mild									
	Moderate									
	Severe									
Induration	None									

Table 51: Number and Percentage of Maternal Subjects Experiencing Solicited Events by Symptom, Maximum Severity, and Treatment Group (continued)

Symptom	Severity	BOOSTRIX (N=X)			Td (N=X)			All Subjects (N=X)		
		n	%	95% CI	n	%	95% CI	n	%	95% CI
	Mild									
	Moderate									
	Severe									
Ecchymosis Measurement (mm)	None									
	Mild									
	Moderate									
	Severe									
Erythema Measurement (mm)	None									
	Mild									
	Moderate									
	Severe									
Induration Measurement (mm)	None									
	Mild									
	Moderate									
	Severe									
Note: N = Number of subjects in the Maternal Safety Population. The denominator for the percentages is the number of subjects with non-missing data for the specific event.										

**Table 52: Number and Percentage of Maternal Subjects Experiencing Solicited Events by Symptom, Severity, Day Post Dosing, and Treatment Group – BOOSTRIX**

BOOSTRIX (N=X)																			
Symptom	Severity	Pre-Dose		Post-Dose		Day 2		Day 3		Day 4		Day 5		Day 6		Day 7		Day 8	
		n	%	n	%	n	%	n	%	n	%	n	%	n	%	n	%	n	%
Any Symptom	None	x	xx	x	xx	x	xx	x	xx	x	xx	x	xx	x	xx	x	xx	x	xx
	Mild																		
	Moderate																		
	Severe																		
	Not Reported																		
Systemic Symptoms																			
Any Systemic Symptom	None																		
	Mild																		

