	Mild									
	Moderate									

Table 81: Number and Percentage of Maternal Subjects Experiencing Pregnancy-Related Events by Symptom, Maximum Severity, and Treatment Group (continued)

Symptom	Severity	BOOSTRIX (N=X)			Td (N=X)			All Subjects (N=X)		
		n	%	95% CI	n	%	95% CI	n	%	95% CI
	Severe									
Preterm Contractions/Labor/Delivery	None									
	Mild									
	Moderate									
	Severe									
Poor Fetal Growth	None									
	Mild									
	Moderate									
	Severe									
Hypertension, Preeclampsia/eclampsia	None									
	Mild									
	Moderate									
	Severe									
Chorioamnionitis	None									
	Mild									
	Moderate									
	Severe									
Postpartum Endometritis	None									
	Mild									
	Moderate									
	Severe									
Gestational Diabetes	None									
	Mild									
	Moderate									

Table 81: Number and Percentage of Maternal Subjects Experiencing Pregnancy-Related Events by Symptom, Maximum Severity, and Treatment Group (continued)

Symptom	Severity	BOOSTRIX (N=X)			Td (N=X)			All Subjects (N=X)		
		n	%	95% CI	n	%	95% CI	n	%	95% CI
	Severe									
Other Pregnancy Related AE	None									
	Mild									
	Moderate									
	Severe									

Note: N = Number of subjects in the Maternal Safety Populations.

**Table 82: Number and Percentage of Infant Subjects Experiencing Infancy-Related Events by Symptom, Maximum Severity, and Treatment Group**

Symptom	Severity	BOOSTRIX (N=X)			Td (N=X)			All Subjects (N=X)		
		n	%	95% CI	n	%	95% CI	n	%	95% CI
Any Neonatal and Infant Events	None	x	xx	x.x, x.x	x	xx	x.x, x.x	x	xx	x.x, x.x
	Mild									
	Moderate									
	Severe									
Preterm Birth	None									
	Mild									
	Moderate									
	Severe									
Birth Weight	None									
	Mild									
	Moderate									
	Severe									
Neonatal Complications in a Term Infant	None									
	Mild									
	Moderate									
	Severe									

Table 82: Number and Percentage of Infant Subjects Experiencing Infancy-Related Events by Symptom, Maximum Severity, and Treatment Group (continued)

Symptom	Severity	BOOSTRIX (N=X)			Td (N=X)			All Subjects (N=X)		
		n	%	95% CI	n	%	95% CI	n	%	95% CI
Other AE in Newborn	None									
	Mild									
	Moderate									
	Severe									
Congenital Abnormalities/Birth Defects	None									
	Mild									
	Moderate									
	Severe									

Note: N = Number of subjects in the Infant Safety Population.

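### Maternal rates of delivery and postpartum events divide by every vaccinated woman, so women lost before delivery count as event-free, and the SAP's denominator rules conflict

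*SAP*

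**What the plan says.** SAP 9.3 counts each subject once per event and states that "the denominator will be the total size of the specified population being analyzed". The rule reaches the pregnancy and infant events because SAP 9.3.2 lists Tables 77 and 78 among its outputs: "Subject incidence and total frequency of pregnancy-or infancy related adverse events by treatment group with 95% CI".

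SAP 6.3.3 defines the Safety population as "all pregnant women who received the study vaccination, and all infants born during the study". It sets no condition on follow-up to delivery. The notes under Tables 77, 79 and 81 give N as the Maternal Safety Population and say nothing further about the denominator. The infant shells (Tables 78, 80 and 82) likewise give only "Number of subjects in the Infant Safety Population".

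Two other places point the other way. SAP 6.1 bases categorical percentages on the non-missing sample size and has tables annotated with the total population. SAP 9 repeats the non-missing basis for safety data. It then says that the "denominator for the percentages may be based on the number of non-missing observations for an assessment", or on the population size, with the choice to be described table by table. The Table 51 footnote on solicited events keeps that promise: "The denominator for the percentages is the number of subjects with non-missing data for the specific event". Tables 77 to 82 have no such footnote.

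Pregnancy-specific events in mothers and infants are a primary safety endpoint, to be described and compared between arms (SAP 3.2.1). SAP 6.5 plans no imputation.

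**The concern.** Preterm delivery, postpartum hemorrhage and postpartum endometritis can be observed only in a woman followed to delivery or beyond. Under SAP 9.3, a vaccinated woman lost before that point adds one to the denominator and nothing to the numerator. For these events she is treated as if she had been followed and had no event.

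The per-arm rate of a primary safety endpoint then falls by the unascertained fraction, and its Clopper-Pearson interval is computed on women who were never observed for the event. If loss differs between arms, the comparison in Table 79 mixes differential follow-up with vaccine effect. Because the SAP also contains a non-missing rule, two analysts could produce different rates from the same data and both cite the plan.

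**Working it through.** The documents give no background rate for any pregnancy or infant event, no number expected to be lost before delivery, and no expected number of unsigned infant pages. The event rates and loss fractions below are assumptions, shown as ranges.

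**Inputs from the documents.** Arms of 133 (BOOSTRIX) and 67 (Td), total 200 (SAP 5). Loss allowance of 15% (Protocol 5.3.5). Protocol 11.2.2 and SAP 5 use the same 15% for exclusion from the per-protocol immunogenicity analysis, deviations included. It is therefore an upper-end proxy for loss before delivery, not an estimate of it.

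**Nearest planned figure.** SAP Table 3 gives the probability of seeing at least one event in an arm, which is 1 − (1 − p)^N. At p = 1% this is 73.7% for N = 133 and 49.0% for N = 67; all eight cells of the table reproduce. With 15% unascertained, 133 × 0.85 ≈ 113 and 67 × 0.85 ≈ 57, and the 1% row becomes 67.9% and 43.6%. For delivery-dependent events, Table 3 therefore assumes that every woman is ascertained.

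**Per-arm rate.** Let u be the fraction of vaccinated women whose outcome is not ascertained. If loss is unrelated to the event, rate shown = true rate × (1 − u).

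| True rate (assumed) | u = 5% | u = 15% |
|---|---|---|
| 5% | 4.75% | 4.25% |
| 10% | 9.5% | 8.5% |
| 15% | 14.25% | 12.75% |

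The shortfall is 5% to 15% in relative terms, or 0.25 to 2.25 percentage points over this grid.

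**Example with intervals.** Eleven BOOSTRIX events among 113 ascertained women are 11/113 = 9.7% (95% Clopper-Pearson CI 5.0 to 16.8). On the full arm they are 11/133 = 8.3% (4.2 to 14.3).

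**Between arms, true rate 10% in both (assumed).**
- Loss 15% and 15%: 8.5% v 8.5%. The risk ratio stays at 1. Where a true difference exists, equal loss leaves the ratio unchanged and shrinks the risk difference by the factor 1 − u.
- Loss 20% BOOSTRIX, 5% Td: 8.0% v 9.5%, risk ratio 0.84.
- Loss 5% BOOSTRIX, 20% Td: 9.5% v 8.0%, risk ratio 1.19.

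**Testing threshold.** Protocol 11.4.2 compares arms on untoward fetal, perinatal and congenital outcomes only if more than 5% of women are affected. Ten affected women are 10/200 = 5.0% (not met), but 10/170 = 5.9% (met) if 200 × 0.85 = 170 are ascertained. SAP 9.5 carries no such threshold, so this matters only where the protocol's rule is followed.

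**The case against.** The strongest reply is that the whole-population denominator is not settled. SAP 6.1 and SAP 9 lean towards non-missing percentages, and SAP 6.1 makes N a column annotation. On that reading, the N under Tables 77 to 82 does not prove what the percentages divide by. This stands in part: the SAP conflicts with itself. It does not remove the point. SAP 9.3 is the specific rule for event incidence and is unqualified, and the statement SAP 9 promises for each table is missing from exactly these tables.

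The second reply is that loss should be small and visible. The protocol provides chart review (7.4), three contact attempts (5.3.4), birth outcomes at early termination (7.6) and an on-call team near the delivery room (7.4.2.2.1). SAP 9.5 describes every effort to follow pregnancies to outcome. Table 9 shows completion by arm, and unknown outcomes can be approximated by subtraction in Table 75. All of this limits the size and helps a careful reader, but the rates, intervals and Fisher tests in Tables 77 and 79 would still use the full denominator.

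A reader might also infer more than the documents support:
- That infants whose mothers do not re-sign are counted as event-free. Protocol 14.3 says that without the signature "it is assumed that consent is not given and the infant will not participate in the post-partum phase of the study", but Tables 10 and 12 start from enrolled infants, and no text places such a child in the Infant Safety Population. Birth outcomes may also be available under the mother's own agreement (inclusion criterion 6). This is an ambiguity, not a shown bias.
- That the four severity rows of Tables 81 and 82 show unknowns coded as 'None'. Table 51 has the same four rows with a non-missing denominator, so the layout shows nothing.
- That every rate is understated. Events recorded before a woman leaves, such as antepartum bleeding or gestational diabetes, still count.

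**Conclusion.** The point holds for maternal events observable only at or after delivery. Under SAP 9.3 and the notes to Tables 77, 79 and 81, their per-arm rates are lowered by the unascertained fraction: an assumed 10% is shown as 9.5% to 8.5% for 5% to 15% loss. This rests on loss being unrelated to the event and on 15% as an upper-end proxy. If few outcomes are missing, as SAP 6.5 expects, the effect is small.

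The downward bias concerns the rate within each arm. It should not be read as a bias of known direction in the comparison: equal loss leaves the risk ratio unchanged, and unequal loss can move it either way. Separately, SAP 9.3 conflicts with SAP 6.1 and SAP 9, and the status of infants without the re-signed page is undefined. Both need settling whatever the amount of loss.

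**What to change.** - **SAP 9.3, 9.5 and Tables 75, 77, 79 and 81.** For delivery and postpartum events, use women with known pregnancy outcome as the denominator. Add an 'Unknown / not ascertained' row by arm. Keep the whole-population rate as a sensitivity analysis, since the ascertained rate assumes that lost women resemble those followed.
- **Tables 78, 80 and 82.** Use live-born infants with that specific outcome ascertained. Do not require postpartum consent or survival to an assessment: re-signing happens after delivery, so such a condition could drop early neonatal deaths.
- **SAP 6.3.3 and Table 12.** State whether infants without the re-signed page belong to the Infant Safety Population.
- **SAP 6.1, 9 and 9.3.** Reconcile the denominator rules, and give Tables 77 to 82 a denominator footnote as in Table 51.

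The cost is SAP text and table shells, with no new data collection. The downside is slightly smaller denominators.

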### 9.3.1. Solicited Events and Symptoms

Systemic solicited adverse events will be collected in maternal subjects pre-vaccination, and systemic and local solicited adverse events will be collected 30 minutes post-vaccination and then daily for 7 days after vaccination and graded on a scale of 0 (absent), 1 (mild), 2 (moderate) and 3 (severe). Systemic events include fatigue, headache, nausea, allergic reaction, myalgia, malaise, arthralgia, feverishness and fever. Local events include pain at injection site, tenderness, ecchymosis, erythema, induration, and measurements of ecchymosis, erythema, and induration ([Table 8](#)).

The proportion of subjects reporting at least one solicited adverse event will be summarized for each solicited adverse event, any systemic symptom, any local symptom, and any symptoms. The 95% CI calculated using Clopper-Pearson methodology from a binomial distribution (SAS Proc Freq with a binomial (exact) option) will be presented and a Fisher's exact test will be performed to test for the difference in the proportion of subjects reporting a solicited adverse event ([Table 49](#) and [Table 50](#)).

For each systemic and local event, any systemic event, any local event, and any solicited event, the maximum severity over 7 days after vaccination will be summarized for the Safety population. The number and percentage of subjects reporting each event will be summarized by the maximum severity and treatment group ([Table 51](#)).

The number of subjects reporting a solicited adverse event will be summarized for each day post vaccination by treatment group in a summary table ([Table 52](#), [Table 53](#), and [Table 54](#)) and graphically in a bar chart ([Figure 225](#) and [Figure 226](#)).

Solicited adverse events by subject will be presented in [Listing 10](#) and [Listing 11](#).

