9.2.2. Reactogenicity (for Vaccine Studies and Some Therapeutic Trials)

Reactogenicity events are AEs that are common and known to occur following administration of this type of study vaccine. The following Toxicity Grading Scales will be used to grade solicited local (injection site) and systemic (subjective and quantitative) reactions:

Table 3: Local (Injection Site) Reactogenicity Grading

Local (Injection Site) Reaction	Mild (Grade 1)	Moderate (Grade 2)	Severe (Grade 3)
Pain	Does not interfere with daily activity	Repeated use of non-narcotic pain reliever > 24 hours or interferes with daily activity	Any use of narcotic pain reliever or prevents daily activity
Tenderness	Discomfort only to deep palpation	Discomfort to light palpation or movement	Significant discomfort to any touch or movement
Ecchymosis (Bruising)*	No interference with daily activity	Some interference with daily activity not requiring medical intervention	Prevents daily activity and requires medical intervention
Erythema (Redness)*	Does not interfere with daily activity	Interferes with daily activity	Prevents daily activity
Induration (Hardness)/Edema (Swelling)*	Does not interfere with daily activity	Interferes with daily activity	Prevents daily activity

Ecchymosis (bruising), erythema (redness), and induration (hardness)/edema (swelling) as analyzed by measurement will be graded as follows:

Table 4: Local (Injection Site) Reactogenicity Measurements

Local (Injection Site) Reaction	Small	Medium	Large
Ecchymosis (Bruising)*	1-50 mm	51-100 mm	> 100 mm
Erythema (Redness)*	1-50 mm	51-100 mm	> 100 mm
Induration (Hardness)/Edema (Swelling)*	1-50 mm	51-100 mm	> 100 mm

*Will not be used as halting criteria.

In addition to grading the measured local reactions at the greatest single diameter, the measurements will be recorded as continuous variables.

Table 5: Subjective Systemic Reactogenicity Grading

Systemic (Subjective)	Mild (Grade 1)	Moderate (Grade 2)	Severe (Grade 3)
Feverishness (Chills/Shivering/Sweating)	No interference with daily activity	Some interference with daily activity not requiring medical intervention	Prevents daily activity and requires medical intervention
Fatigue (Tiredness)	No interference with daily activity	Some interference with daily activity	Significant; prevents daily activity

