9.5. Halting Rules

For pregnant women, further enrollment and study vaccinations will be halted for DSMB review/recommendation if any of the following are reported:

- Any subject experiences ulceration, abscess, or necrosis at the injection site related to study product administration.
- Any subject experiences laryngospasm, bronchospasm, or anaphylaxis within 1 day after administration of study product that is considered related to study product.

- Two or more subjects experience generalized urticaria within 3 days after administration of study product that is considered related to study product.
- Any subject experiences a study vaccine-related SAE from the time of study vaccination through subject's last study visit.
- Any subject experiences acute weakness of limbs and/or cranial nerve innervated muscles (description of potential signal of GBS) after administration of study vaccine.

For pregnant women, this study will also be halted for DSMB review/recommendation if, within 7 days after administration of the study vaccination, any of the following occurs:

- 5% or more of subjects (with a minimum of 5 subjects) who received study vaccine experience the same severe (Grade 3) study vaccine-related injection site reaction.
- 5% or more of subjects (with a minimum of 5 subjects) who received study vaccine experience the same severe (Grade 3) study vaccine-related subjective systemic reaction with the exception of allergic reaction, for which the severity (grade) is corroborated by study personnel.
- 5% or more of subjects (with a minimum of 5 subjects) who received study vaccine experience the same severe (Grade 3) study vaccine-related quantitative systemic reaction.
- 5% or more of subjects (with a minimum of 5 subjects) who received study vaccine experience the same severe (Grade 3) pregnancy-related AEs, as found in [Section 9.2.4](#), that are deemed study-vaccine related.

Grading scales for solicited local (injection site) and systemic (subjective and quantitative) reactions are included in [Section 9.2.2](#). Solicited injection site measurements will not be used to halt the study.

If any of the halting rules are met following any subject receipt of study vaccination, then this study will not continue with the remaining enrollments or study vaccinations without a review by and recommendation from the DSMB to proceed.

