## 12.2.2 Displays of Adverse Events

**Table 8:      Solicited Adverse Event Grading Scale**

	Mild (Grade 1)	Moderate (Grade 2)	Severe (Grade 3)
Local (Injection Site) Reaction			
Pain	Does not interfere with daily activity	Repeated use of non-narcotic pain reliever > 24 hours or interferes with daily activity	Any use of narcotic pain reliever or prevents daily activity
Tenderness	Discomfort only to deep palpation	Discomfort to light palpation or movement	Significant discomfort to any touch or movement
Echymosis (Bruising) ^	No interference with daily activity	Some interference with daily activity not requiring medical intervention	Prevents daily activity and requires medical intervention
Erythema (Redness) ^	Does not interfere with daily activity	Interferes with daily activity	Prevents daily activity
Induration (Hardness)/Edema (Swelling) ^	Does not interfere with daily activity	Interferes with daily activity	Prevents daily activity
Echymosis (Bruising) Measurement ^	1-50 mm	51-100 mm	> 100 mm
Erythema (Redness) Measurement ^	1-50 mm	51-100 mm	> 100 mm
Induration (Hardness)/Edema (Swelling) Measurement ^	1-50 mm	51-100 mm	> 100 mm
Systemic (Subjective)			
Feverishness (Chills/Shivering/Sweating)	No interference with daily activity	Some interference with daily activity not requiring medical intervention	Prevents daily activity and requires medical intervention
Fatigue (Tiredness)	No interference with daily activity	Some interference with daily activity	Significant; prevents daily activity
Malaise (General Unwell Feeling)	No interference with daily activity	Some interference with daily activity not requiring medical intervention	Prevents daily activity and requires medical intervention
Myalgia (Body Aches/Muscular Pain)*	No interference with daily activity	Some interference with daily activity	Significant; prevents daily activity
Arthralgia (Joint Pain)*	No interference with daily activity	Some interference with daily activity not requiring medical intervention	Prevents daily activity and requires medical intervention
Headache	No interference with daily activity	Repeated use of non-narcotic pain reliever > 24 hours or some interference with daily activity	Significant; any use of narcotic pain reliever or prevents daily activity
Nausea	No interference with daily activity	Some interference with daily activity	Prevents daily activities

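### The SAP relabels the protocol's Small/Medium/Large reaction sizes as Mild/Moderate/Severe and counts them as local events, so a wide but non-limiting reaction is reported as severe in the composite severity rows

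*SAP*

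**What the plan says.** **Protocol 9.2.2.** Table 3 grades five local reactions (pain, tenderness, ecchymosis, erythema, induration/edema) as Mild, Moderate or Severe. For the last three, the grade depends on interference with daily activity. Diameter is handled in a second table, "Table 4: Local (Injection Site) Reactogenicity Measurements", whose columns are Small (1-50 mm), Medium (51-100 mm) and Large (over 100 mm). The lead-in to that table says these reactions "as analyzed by measurement will be graded as follows". The protocol then adds: "In addition to grading the measured local reactions at the greatest single diameter, the measurements will be recorded as continuous variables".

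**SAP Table 8.** The same millimetre bands appear as extra rows, for example "Erythema (Redness) Measurement", under the columns Mild (Grade 1), Moderate (Grade 2) and Severe (Grade 3).

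**SAP 9.3.1.** Solicited events are graded 0 to 3, and the text reads: "Local events include pain at injection site, tenderness, ecchymosis, erythema, induration, and measurements of ecchymosis, erythema, and induration". The planned summary is: "For each systemic and local event, any systemic event, any local event, and any solicited event, the maximum severity over 7 days after vaccination". The shells of Tables 51-54 give each measurement None/Mild/Moderate/Severe rows inside the local block.

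**SAP section 15.** Changes in the planned analyses are given as not applicable.

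**Halting.** In protocol Table 3 the asterisk is on the functional rows for ecchymosis, erythema and induration/edema. The note for it, printed below Table 4, says that marked items are not halting criteria. Protocol 9.5 halts on the same related Grade 3 injection site reaction in 5% or more of vaccinated subjects (minimum 5) within 7 days, and states one exemption: "Solicited injection site measurements will not be used to halt the study".

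**The concern.** Frequency and severity of solicited reactions is a primary tolerability outcome in both documents (section 3.2.1 of each). The protocol uses the words mild, moderate and severe for functional impact and a different set of words for size. The SAP merges the two and then takes a maximum across them. A reader of the study report who sees a severe rate under Any Local Symptom or Any Symptom would take it to mean that daily activity was prevented. Part of that rate could instead be women with a wide patch of redness who carried on as normal. The change is neither recorded nor justified in the SAP.

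The halting mark raises a separate question on the same rows. If the mark in Table 3 means what its note says, three of the five local reactions do not count towards the 5% rule. If 9.5 is read alone, their functional grades do count and only the measurements are left out.

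**Working it through.** There is no stated figure to reproduce; this is a check of grading rules.

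**1. Apply both rules to a reaction that does not interfere with activity (functional Grade 1).** The SAP rule is: Any Local severity = maximum of all local grades, size included. The alternative uses the functional grade only. Assume no other local event.

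| Diameter | Protocol Table 3 | Protocol Table 4 | SAP Table 8 size grade | Any Local, SAP rule | Any Local, functional only | Any Local yes/no, SAP rule / functional only |
|---|---|---|---|---|---|---|
| 10 mm | Mild (1) | Small | 1 | max(1,1) = 1 Mild | 1 Mild | yes / yes |
| 60 mm | Mild (1) | Medium | 2 | max(1,2) = 2 Moderate | 1 Mild | yes / yes |
| 110 mm | Mild (1) | Large | 3 | max(1,3) = 3 Severe | 1 Mild | yes / yes |

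The severity distribution changes. The yes/no indicator does not, because a measurable reaction that causes no interference already has functional Grade 1.

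**2. Effect per woman.** With the planned arm sizes, one reclassified woman moves the severe rate by 1/133 = 0.75 percentage points in BOOSTRIX and by 1/67 = 1.5 points in Td. She counts once even if both redness and swelling exceed 100 mm. She does not move the composite if she already has another Grade 3 event in it.

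**3. Illustration of scale, by assumption only.** The documents give no rate of large, non-limiting reactions. Take a severe rate without size of b = 1.6% (the severe injection-site pain rate that protocol 2.3.1 cites for US adults) and an assumed extra share q = 0.5% to 3% with more than 100 mm and no functional Grade 3. Expected severe women = n × (b + q).

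- BOOSTRIX: 133 × 0.016 = 2.1 without size; 133 × 0.021 = 2.8 to 133 × 0.046 = 6.1 with size.
- Td: 67 × 0.016 = 1.1 without size; 67 × 0.021 = 1.4 to 67 × 0.046 = 3.1 with size.

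**4. Halting passages side by side.**

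| Place | Functional grades of ecchymosis, erythema, induration | Measurements |
|---|---|---|
| Protocol Tables 3 and 4, with note | Marked as not for halting | Marked as not for halting |
| Protocol 9.5 | No exemption stated | Exempt |
| SAP Table 8 | Rows carry a mark; the footnote symbol is garbled in the text available to us, so the link is inferred | Same mark |

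The 5% rule with its minimum of 5 is met by 5 women for up to 100 vaccinated (5% of 100 = 5), and by a growing number after that.

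**The case against.** **The protocol itself grades size.** It does: it introduces its tables as grading scales and says that the measured reactions are graded. A reader might infer that the SAP invents a size grade. That is not supported. What remains is narrower: the labels change from Small/Medium/Large to Mild/Moderate/Severe, and the sizes are pooled with the functional grades.

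**No protocol-defined composite is broken.** Protocol 11.4.2 defines the any-injection-site summary as a yes/no proportion and gives no rule for a composite severity grade. This stands, and it is why the Fisher tests in Tables 49-50 are hardly touched. It does not remove the problem in Tables 51-54, where the SAP adds a severity composite using words that protocol Table 3 reserves for functional impact.

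**Nothing is hidden by symptom.** Functional and measurement rows are separate, so a severe size entry can be traced there. It cannot be traced in the two composite rows. The SAP gives no explicit derivation of Any Local Symptom; inclusion of the measurements follows from its definition of local events and from the shells. If something else is intended, the SAP should say so.

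**The mark in Table 3 may refer to measurements only.** The note is printed beneath Table 4, and that reading would agree with 9.5. It leaves unexplained why the asterisks are on the functional rows of Table 3.

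**Conclusion.** The point holds for the composite severity rows. As written, the SAP reports a functionally Grade 1 reaction as Severe above 100 mm and as Moderate at 51-100 mm. It does so in the measurement row and, absent a worse event, in Any Local Symptom and Any Symptom in Tables 51-54. Figure 226, which shows maximum local severity by day, would follow if it uses the same derivation; its image is not available.

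The size of the effect is unknown. It is about 0.75 points per reclassified woman in BOOSTRIX and 1.5 in Td, and the number of such women cannot be taken from the documents.

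Three stronger readings are tempting but unsupported:

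- That the severe rate would move from 0 to 1-3%, using the cited severe erythema (1.6%) and induration (1.4%) rates. The protocol does not say that those rates are size grades, and they come from 14 days of monitoring. Starting from 0 also ignores other severe local events: at 1.6% severe pain alone, the chance of at least one in 133 is 1 - (1 - 0.016)^133 = 88%.
- That the treatment comparison is biased. The yes/no tests are essentially unchanged.
- That 9.5 counts every Grade 3 local reaction. It requires the same related reaction in at least 5% of vaccinated subjects, with a minimum of 5.

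The halting inconsistency is real in the protocol text and probable in the SAP. This review takes no view on which passage is right.

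**What to change.** 1. In SAP Table 8 and Tables 51-54, and in Figure 226 where it applies, label the three measurement rows None/Small/Medium/Large, as in protocol Table 4.
2. Add one derivation line to SAP 9.3.1: the maximum severity of Any Local Symptom and Any Symptom comes from the functional grades only. If the sponsor prefers severity to include size, show both versions and record the departure, with the reason, in SAP section 15.
3. Reconcile the marks in protocol Table 3 and SAP Table 8 with protocol 9.5, so that all three name the same local reactions as counting or not counting towards halting.

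The cost is a few table labels, one sentence on derivation and one clarifying edit on halting. No data collection changes, because functional grades and diameters are already recorded separately.
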